2.1.3 Conclusion

The safe starting dose in this study is determined to be This dose is not expected to trigger any relevant or unacceptable biological activities.

An exposure threshold is defined

The following dose escalation scheme is planned:
as single oral dose. Dose escalation will be guided by interim PK measurements (see [Section 7.3.4](#)) and projected exposure levels.

2.2 TRIAL OBJECTIVES

The primary objective of this trial is to investigate the safety and tolerability of BI 1323495 in healthy male subjects following oral administration of single rising doses.

Secondary objectives are the exploration of the pharmacokinetics (PK) including dose proportionality and pharmacodynamics (PD) of BI 1323495 after single dosing and the assessment of the PK/PD relationship.

Proprietary confidential information © 2018 Boehringer Ingelheim International GmbH or one or more of its affiliated companies

A description of the endpoints to be determined, and the observations along with specific information as how to collect the data for that information, is provided in [Section 5](#).

2.3 BENEFIT - RISK ASSESSMENT

Participation in this study is without any (therapeutic) benefit for healthy subjects. Their participation in the study, however, is of major importance to the development of a new orally available drug, which might improve the therapy in patients with

The subjects are exposed to the risks of the study procedures and the risks related to the exposure to the trial medication.

2.3.1 Procedure-related risks

The use of an indwelling venous catheter for the purpose of blood sampling may be accompanied by mild bruising and also, in rare cases, by transient inflammation of the wall of the vein. In addition, in rare cases a nerve might be injured while inserting the venous catheter, potentially resulting in paresthesia, reduced sensibility, and/or pain for an indefinite period. The same risks apply to venipuncture for blood sampling.

The total volume of blood withdrawn during the entire study per subject will not exceed the volume of a normal blood donation (500 mL). No health-related risk to healthy subjects is expected from this blood withdrawal.

2.3.2 Drug-related risks

Factors of risk may derive from particular knowledge or the lack thereof, regarding (1) the mode of action, (2) the nature of the target, (3) the relevance of animal models and/or (4) findings in non-clinical safety studies.

2.3.2.5 Drug-induced liver injury

Although rare, a potential for drug-induced liver injury (DILI) is under constant surveillance by sponsors and regulators. Therefore, this trial requires timely detection, evaluation, and follow-up of laboratory alterations in selected liver laboratory parameters to ensure subjects' safety, see also [Section 5.2.2.1](#), adverse events of special interest.

2.3.3 Safety measures

- Dose selection was based on a sound preclinical package including 4 week toxicological studies (see [Section 1.2.3](#)) and non-clinical pharmacology data ([Section 1.2.1](#)).

Careful selection of starting dose as described in [Section 2.1](#).

Dose escalation will be shallow with an increase of not more than 1.5 fold at the higher dose groups.

Proprietary confidential information © 2018 Boehringer Ingelheim International GmbH or one or more of its affiliated companies

- Measurement of BI 1323495 plasma concentrations and preliminary determination of PK parameters (C_{max} , AUC_{0-24} , see [Section 7.3.4](#)). For precautionary reasons, drug plasma concentrations in this healthy volunteer trial should not exceed a C_{max} of _____ or an AUC_{0-24} of _____ and will be considered as a preliminary threshold (see [Section 2.1](#)). Further dose progression would only be allowed after a safety interim analysis and filing and approval of a substantial CTP amendment.
- For safety reasons, each dose group of 8 subjects (6 on active, 2 on placebo) will be divided into three cohorts. In the 1st cohort only 2 subjects will be treated: one subject will receive active treatment, the other subject will receive placebo. If BI 1323495 treatment is safe and well tolerated in this first cohort, the following 2 subjects on active will be treated in the 2nd cohort with drug administration occurring not earlier than 24 hours after the first subject of the dose level received active treatment. The remaining 4 subjects (either active or placebo) are the third cohort and will be treated no sooner than 48 hours following the 1st cohort. Within each cohort, a time interval of at least 10 min will be maintained between administrations of study drug.

This design ensures that between first and second active dose of each dose level there is a time interval of at least 24 hours, which is expected to be sufficient to detect relevant first acute effects of BI 1323495.

- Only if the respective dose of BI 1323495 was safe and showed acceptable tolerability and if no stopping criterion was met (see [Section 3.3.4.2](#)), the next higher dose will be given at least 6 days later (referring to the 1st subject of each dose group). A documented Safety Review must take place prior to each dose escalation (see [Section 3.1](#)).
- An extensive safety laboratory will be performed (see [Section 5.2.3](#)).
- A thorough ECG monitoring including continuous ECG measurement over 4 hours post-dose and repeated 12-lead ECGs during the observation period following drug administration. Dose escalation would be stopped as soon as at least 2 subjects at one dose level showed relevant QT prolongation (see [Section 3.3.4.2](#) for details).
- The subjects will stay at the trial site (BI Human Pharmacology Centre) for at least 34 hours after study drug administration. Based on an anticipated half-life of BI 1323495 of approximately _____ this is expected to cover the period of highest risk / peak effect.
- During in-house confinement the subjects will be under medical observation and thoroughly monitored for both expected and unexpected adverse events.

In summary, although not tested in humans to date, BI 1323495 has the potential to become an oral treatment for patients with _____. Based upon preclinical data for BI 1323495 and clinical information from competitor compounds as well as the implemented safety measures described above, healthy subjects will not be exposed to undue risks in relation to the important information expected from this trial as a basis for further clinical development of this compound. Healthy volunteers are not expected to have any direct benefit from participation in this first-in-man clinical trial with BI 1323495. Considering the medical need of the development of an effective treatment for patients with _____ the Sponsor considers

Proprietary confidential information © 2018 Boehringer Ingelheim International GmbH or one or more of its affiliated companies

that the benefit outweighs the potential risks and justifies exposure of healthy human volunteers.

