3. DESCRIPTION OF DESIGN AND TRIAL POPULATION

3.1 OVERALL TRIAL DESIGN AND PLAN

This single-rising dose trial is designed as single-blind, partially randomised, and placebo-controlled within parallel dose groups.

A total of 64 healthy male subjects is planned to participate in the trial, according to 8 sequential groups comprising 8 subjects per group. However, additional subjects may be entered to allow testing of additional doses on the basis of experience gained during the trial conduct (e.g., preliminary PK data), provided the planned and approved highest dose will not be exceeded. Thus, the actual number of subjects entered may exceed 64, but will not exceed 80 subjects entered. Such changes may be implemented via non-substantial CTP Amendments provided additional doses are used for the further evaluation of pharmacokinetics or pharmacodynamics in the absence of new safety signals. The addition of dose groups to further evaluate safety findings may be implemented only after notification of a substantial amendment.

Within each dose group, 6 subjects will receive the active drug and 2 will receive placebo. Only one dose is tested within each dose group. Each dose group will consist of 3 cohorts which will be treated subsequently for safety reasons.

The dose groups to be evaluated are outlined in Table 3.1: 1 below.

Table 3.1: 1 Dose groups

The dose groups will be investigated consecutively in ascending order of doses, maintaining a time interval of at least 6 days between the first drug administration in the previous dose group and the first drug administration of the subsequent dose group. The decision to proceed to the next dose group will be based upon the safety, tolerability, and pharmacokinetic data of the preceding dose groups. The next dose will only be given if, in the opinion of the investigator, no safety concerns arose in the preceding dose group (i.e., no dose-limiting events occurred) and if none of the pre-specified trial-specific stopping criteria were met (refer to [Section 3.3.4.2](#)).

A documented Safety Review must take place prior to each dose escalation. Furthermore, an unscheduled safety review meeting can be requested any time for any reasonable cause by the Principal Investigator (or an authorised deputy) or the sponsor of the study, e.g. because of any unforeseen adverse events, etc. Dose escalation will only be permitted if no safety

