Proprietary confidential information © 2018 Boehringer Ingelheim International GmbH or one or more of its affiliated companies

concerns exist in the opinion of the Principal Investigator (or an authorised deputy) and the trial clinical monitor (or an authorised deputy).

Although no formal Safety Review meeting will take place within a given dose group, safety will be continuously monitored during this trial, and an individual will only be dosed in the absence of any safety concern (i.e., no dose-limiting events occurred) and if none of the pre-specified trial-specific stopping criteria have been met (refer to [Section 3.3.4.2](#)).

The minimum data set for review consists of the following data:

- AEs in the current* and preceding dose groups including clinically relevant findings from ancillary safety testing listed below up to at least 48 h post-dosing.
Note: AEs may be ongoing at the time of Safety Reviews and AE information may be subject to change prior to Database Lock.
- Vital signs in the current* and preceding dose groups up to at least 48 h post-dosing
- Clinical laboratory tests in the current* and preceding dose groups up to at least 24 hours post-dose
- Preliminary PK data for selected time points as per [Section 7.3.4](#)
- Check of criteria for stopping subject treatment as per [Section 3.3.4.1](#)

**"Current dose group" means: all subjects of that dose group with at least 4 subjects being on active treatment.

The decision to escalate the dose will be made jointly by the Principal Investigator (or an authorised deputy) and the trial clinical monitor (or an authorised deputy) after in-depth analysis of all available safety data, especially SAEs (if occurred), AEs, and out-of-range laboratory results (if considered clinically significant). Safety Reviews can be conducted face-to-face or by video/telephone conference. The trial clinical monitor is responsible for organization and minutes of the reviews. Minutes will be signed off by the Principal Investigator (or an authorised deputy) and filed in the ISF and TMF.

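### Cohort 3 is timed only from cohort 1, so the nominal gap of about 24 h after cohort 2 is not guaranteed

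*Protocol*

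**What the plan says.** Protocol Section 2.3.3 sets two minimum times, both counted from cohort 1.

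- Cohort 1 is one active and one placebo subject.
- Cohort 2 is two active subjects, "with drug administration occurring not earlier than 24 hours after the first subject of the dose level received active treatment". No latest time is given.
- The remaining four subjects "are the third cohort and will be treated no sooner than 48 hours following the 1st cohort". Section 7.5 allocates them 3:1, so three are active.

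On spacing between individuals: "Within each cohort, a time interval of at least 10 min will be maintained between administrations of study drug". For the interval between the first and second active dose the section says that "there is a time interval of at least 24 hours, which is expected to be sufficient to detect relevant first acute effects of BI 1323495". Its explicit condition that treatment was safe and well tolerated is written for the step from cohort 1 to cohort 2.

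Section 3.1 adds order but no interval: "Each dose group will consist of 3 cohorts which will be treated subsequently for safety reasons". It also states: "Although no formal Safety Review meeting will take place within a given dose group, safety will be continuously monitored during this trial". The same sentence makes each individual's dosing conditional on there being no safety concern and no stopping criterion met. Section 3.1 allows an unscheduled safety review on request. Between dose groups it requires "maintaining a time interval of at least 6 days between the first drug administration in the previous dose group" and the first administration in the next. The SAP (Section 6.1) gives group sizes only and nothing on cohort timing.

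**The concern.** Staggered dosing is a named safety measure in this first-in-human trial. Cohort 2 works as a second step only if its two active subjects are watched for some time before three more active subjects are dosed. The nominal calendar provides about a day, but the wording does not require it, because cohort 3 is tied to cohort 1 and cohort 2 may move later without limit.

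A slip with no safety cause is plausible. Subjects are admitted on the morning of Day 1 (Section 6.2.2), must have fasted overnight (4.1.4), and have a drug screen and a breath alcohol test before dosing (5.2.3). A failed check or a no-show could move a cohort 2 subject to the next morning. If cohort 3 keeps its date, part or all of the observation time after cohort 2 is lost. The same wording governs all eight planned dose groups, including the highest.

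**Working it through.** **Group composition.** Active: 1 + 2 + 3 = 6. Placebo: 1 + 0 + 1 = 2. Total 8 per group, and 8 × 8 = 64, which matches the planned number. No power formula is involved.

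**Inputs.** Cohort 2 no earlier than 24 h after the first active dose, cohort 3 no earlier than 48 h after cohort 1, and 10 min between doses within a cohort (2.3.3). Cohort 1 doses active then placebo (7.5). AEs and vital signs up to at least 48 h are needed for the Safety Review, and 6 days = 144 h separate first doses of consecutive groups (3.1).

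**Assumptions.** Doses are given at the minimum spacing. The 10 min also applies between the last cohort 2 dose and the first cohort 3 dose; the protocol states it only within cohorts. The review needs 48 h data on all eight subjects.

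**Clock.** The first active dose is at 0 h 00 and the cohort 1 placebo at 0 h 10. The 48 h can be counted from the first cohort 1 subject (reading A) or the last (reading B). Gap = first cohort 3 dose − last cohort 2 dose. Review data complete = last cohort 3 dose + 48 h.

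| Schedule | Cohort 2 doses | Cohort 3 doses | Gap | Most active dosed on one morning | Review data complete |
|---|---|---|---|---|---|
| Current, nominal, reading A | 24 h 00, 24 h 10 | 48 h 00 to 48 h 30 | 23 h 50 | 3 of 6 | 96 h 30 |
| Current, nominal, reading B | 24 h 00, 24 h 10 | 48 h 10 to 48 h 40 | 24 h 00 | 3 of 6 | 96 h 40 |
| Current, cohort 2 one day late, cohort 3 on its date | 48 h 00, 48 h 10 | 48 h 20 to 48 h 50 | 10 min | 2 + 3 = 5 of 6 | 96 h 50 |
| With added 24 h rule, nominal | 24 h 00, 24 h 10 | 48 h 10 to 48 h 40 | 24 h 00 | 3 of 6 | 96 h 40 |
| With added 24 h rule, one day late | 48 h 00, 48 h 10 | 72 h 10 to 72 h 40 | 24 h 00 | 3 of 6 | 120 h 40 |
| With added 24 h rule, two days late | 72 h 00, 72 h 10 | 96 h 10 to 96 h 40 | 24 h 00 | 3 of 6 | 144 h 40 |

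**Partial slips.** If only one cohort 2 subject moves to the cohort 3 morning, 1 + 3 = 4 of 6 active subjects are dosed that morning. Ignoring the 10 min steps, with cohort 2 at time t between 24 h and 48 h and cohort 3 at 48 h, the gap is 48 − t: 18 h at t = 30 h, 12 h at 36 h, 1 h at 47 h. The guaranteed minimum is effectively zero.

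**Room before the next dose group.** With the added rule, a one-day slip leaves 144 h − 120 h 40 = 23 h 20, which must also hold data preparation and the documented Safety Review. A two-day slip overshoots by 144 h 40 − 144 h = 40 min. As subjects are admitted in the morning, that could cost about a day.

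**The case against.** The strongest reply is that nothing the protocol promises fails. The 24 h between first and second active dose holds in every row above, and in the slipped case the first active subject has been observed for about 48 h. A reader might infer that the stagger contradicts itself or that its guarantee is broken. The documents do not support that: the 24 h statement is made for the first-to-second step only, and carrying it over to cohorts 2 and 3 is a design preference. This stands.

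Also, cohorts treated one after another for safety reasons are hardly meant to be merged, and an investigator who knows the allocation (4.1.5.2) would probably not dose five active subjects within an hour. As a reading of intent this is fair, but intent sets no interval.

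Other controls remain: the per-subject condition, the stopping rules (3.3.4.2), the unscheduled review, continuous ECG over 4 h, and the in-house stay: "The subjects will stay at the trial site (BI Human Pharmacology Centre) for at least 34 hours after study drug administration". A reader might infer that the stopping rules are disabled when few subjects have been observed. They are not the binding control here, since the per-subject condition can act on a single case. It also holds cohort 3 if cohort 2 was delayed by a safety concern, so the gap concerns logistical slips. What survives is that all these controls respond to a signal already seen, and none sets time for one to appear.

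Finally, the anticipated half-life is redacted, so whether a second 24 h suits this drug's time course cannot be judged from the public text.

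**Conclusion.** The point holds as a low-priority improvement. No readable text secures an observation period after cohort 2. The nominal gap of 23 h 50 to 24 h 00 is sound, but it depends on cohort 2 keeping its date. In the extreme permitted case, a full-day slip of cohort 2 with cohort 3 unmoved, five of six active subjects could be dosed on one morning with one active subject observed beforehand. The 10 min gap in that case rests on the assumed spacing across cohorts.

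A reader might want to state how much chance of detecting an acute effect is lost. The documents give neither an event rate nor a slip frequency, so no such figure is supported. The Flow Chart and the content of Table 3.1: 1 are not readable and could already hold the missing interval, so confidence is medium.

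**What to change.** In the cohort-timing bullet of Protocol Section 2.3.3, state that cohort 3 is treated no sooner than 48 h after cohort 1 and no sooner than 24 h after the last cohort 2 dose. The 24 h is the period the protocol already considers adequate for first acute effects. If the Flow Chart or Table 3.1: 1 already sets such an interval, repeat it there.

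The cost is one sentence and a nominal shift of 10 min (reading A) or none (reading B). The downside is that cohort 3 slips whenever cohort 2 does. A one-day slip still fits before the next dose group, though without generous slack; a two-day slip could push that group back by about a day. The preliminary PK step need not move: Section 7.3.4 accepts data from two active subjects, and cohorts 1 and 2 supply three.

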3. DESCRIPTION OF DESIGN AND TRIAL POPULATION

3.1 OVERALL TRIAL DESIGN AND PLAN

This single-rising dose trial is designed as single-blind, partially randomised, and placebo-controlled within parallel dose groups.

A total of 64 healthy male subjects is planned to participate in the trial, according to 8 sequential groups comprising 8 subjects per group. However, additional subjects may be entered to allow testing of additional doses on the basis of experience gained during the trial conduct (e.g., preliminary PK data), provided the planned and approved highest dose will not be exceeded. Thus, the actual number of subjects entered may exceed 64, but will not exceed 80 subjects entered. Such changes may be implemented via non-substantial CTP Amendments provided additional doses are used for the further evaluation of pharmacokinetics or pharmacodynamics in the absence of new safety signals. The addition of dose groups to further evaluate safety findings may be implemented only after notification of a substantial amendment.

Within each dose group, 6 subjects will receive the active drug and 2 will receive placebo. Only one dose is tested within each dose group. Each dose group will consist of 3 cohorts which will be treated subsequently for safety reasons.

The dose groups to be evaluated are outlined in Table 3.1: 1 below.

Table 3.1: 1 Dose groups

The dose groups will be investigated consecutively in ascending order of doses, maintaining a time interval of at least 6 days between the first drug administration in the previous dose group and the first drug administration of the subsequent dose group. The decision to proceed to the next dose group will be based upon the safety, tolerability, and pharmacokinetic data of the preceding dose groups. The next dose will only be given if, in the opinion of the investigator, no safety concerns arose in the preceding dose group (i.e., no dose-limiting events occurred) and if none of the pre-specified trial-specific stopping criteria were met (refer to [Section 3.3.4.2](#)).

A documented Safety Review must take place prior to each dose escalation. Furthermore, an unscheduled safety review meeting can be requested any time for any reasonable cause by the Principal Investigator (or an authorised deputy) or the sponsor of the study, e.g. because of any unforeseen adverse events, etc. Dose escalation will only be permitted if no safety

Proprietary confidential information © 2018 Boehringer Ingelheim International GmbH or one or more of its affiliated companies

concerns exist in the opinion of the Principal Investigator (or an authorised deputy) and the trial clinical monitor (or an authorised deputy).

Although no formal Safety Review meeting will take place within a given dose group, safety will be continuously monitored during this trial, and an individual will only be dosed in the absence of any safety concern (i.e., no dose-limiting events occurred) and if none of the pre-specified trial-specific stopping criteria have been met (refer to [Section 3.3.4.2](#)).

The minimum data set for review consists of the following data:

- AEs in the current* and preceding dose groups including clinically relevant findings from ancillary safety testing listed below up to at least 48 h post-dosing.
Note: AEs may be ongoing at the time of Safety Reviews and AE information may be subject to change prior to Database Lock.
- Vital signs in the current* and preceding dose groups up to at least 48 h post-dosing
- Clinical laboratory tests in the current* and preceding dose groups up to at least 24 hours post-dose
- Preliminary PK data for selected time points as per [Section 7.3.4](#)
- Check of criteria for stopping subject treatment as per [Section 3.3.4.1](#)

**"Current dose group" means: all subjects of that dose group with at least 4 subjects being on active treatment.

The decision to escalate the dose will be made jointly by the Principal Investigator (or an authorised deputy) and the trial clinical monitor (or an authorised deputy) after in-depth analysis of all available safety data, especially SAEs (if occurred), AEs, and out-of-range laboratory results (if considered clinically significant). Safety Reviews can be conducted face-to-face or by video/telephone conference. The trial clinical monitor is responsible for organization and minutes of the reviews. Minutes will be signed off by the Principal Investigator (or an authorised deputy) and filed in the ISF and TMF.

The investigator is allowed to alter the scheduled dose levels (e.g. add low and/or intermediate dose levels) on the basis of experience gained during the study, provided the planned and approved highest dose is not exceeded. In this case, the total number of subjects in this trial might increase. The investigator and/or the sponsor should stop dose escalation in case the safety evaluation leads to concerns that would not allow higher dosing.

An overview of all relevant trial activities is provided in the [Flow Chart](#). For visit schedules and details of trial procedures at selected visits, refer to [Sections 6.1](#) and [6.2](#), respectively.

